5.7 Duration of Therapy and Criteria for Removal from Study

Radiotherapy will be delivered in a total of 5 fractions. Treatments extending over a weekend period are allowed.

In the absence of treatment delays due to adverse event(s), treatment may continue or until one of the following criteria applies:

- Patients unable to tolerate radiation therapy
- Intercurrent illness that prevents further administration of treatment,

- Unacceptable adverse event(s),
- Patient decides to withdraw from the study, or
- General or specific changes in the patient's condition render the patient unacceptable for further treatment in the judgment of the investigator.

5.8 *Duration of Follow Up*

Patients will be followed up 30 days post-surgery. There will be a follow up every 3 months for 5 years post-surgery or until death, whichever occurs first. Patients removed from study for unacceptable adverse events will be followed until resolution or stabilization of the adverse event.

6 *Correlative/Special Studies*

Paraffin-embedded tissue block, PBMCs, plasma will be collected for future translational research analyses for predictors of toxicity and response following radiotherapy. Note: Testing of banked specimens will not occur until an amendment to this treatment protocol is reviewed and approved in accordance with IRB policies.

7 *Data Reporting / Regulatory Considerations*

7.1 *Data Collection*

The data collection plan for this study is to utilize REDCap to capture all treatment, toxicity, efficacy, and adverse event data for all enrolled patients.

7.2 *REDCap*

REDCap (Research Electronic Data Capture) is a free data management software system that is fully supported by the Weill-Cornell Medical Center CTSC. It is a tool for the creation of customized, secure data management systems that include Web-based data-entry forms, reporting tools, and a full array of security features including user and group based privileges, authentication using institution LDAP system, with a full audit trail of data manipulation and export procedures. REDCap is maintained on CTSC-owned servers that are backed up nightly and support encrypted (SSL-based) connections. Nationally, the software is developed, enhanced and supported through a multi-institutional consortium led by the Vanderbilt University CTSA.

7.3 *Data Management*

All patient data will be entered and maintained in REDCap. These data include clinical data and all patient safety data. The REDCap provides audit trails that track creation and modification of records that include user ID and timestamp. Once entered, the data is subjected to validation procedures that are executed either immediately or upon saving the eCRF page or during the batch validation process. Validation failures that are identified before the page is saved can be corrected immediately. Validation failures during saving of the eCRF page and during batch validation processes will generate a discrepancy. Depending on the database account privileges, the data managers may be able to correct a discrepancy or if not, route it to the project data manager at WCMC who can take appropriate action to correct the problem. Once the discrepancy is closed, by marking “resolved” or “irresolvable”, the data is marked clean and an audit trail is generated by the system.

All key end points will be source verified by a second person at each site and errors will be corrected. Once the data is verified and all discrepancies are closed, the data can be locked/frozen. Locking and freezing can be done at different granular levels and will follow institutional SOPs and any specific requirements for the project.

Security measures that will be taken in order to protect patient data will include firewall technology and database level security which will be achieved by assigning roles and privileges to different levels of users and by requiring that the users authenticate themselves using user id and password. Additional security for data transfer between remote clients and servers will be achieved by using digital certificates/SSL. All data will be backed-up to tape periodically according to the Institutional SOPs. All data will be stored for at least 5 years following the termination of this study.

7.4 *Regulatory Considerations*

All protocol amendments and consent form modifications will be made by the Principal Investigator.

8 *Statistical Considerations*

The primary endpoint for this trial will be successful completion of radical prostatectomy after SBRT without a post-operative DLT of grade 3 or higher within 30 days after prostatectomy.

8.1 *Study Design/Endpoints*

This is a single-arm study including two parts. Part 1 will be a modified dose

escalation and de-escalation study to determine maximum tolerated dose (MTD) and the recommended phase II dose (RP2D) based on acute toxicity measures. Part 2 will be a cohort expansion study to further evaluate the safety and tolerability of the RP2D based on toxicities measured at 1 year.

In part 1 of the study, a modified dose escalation and de-escalation design with an expansion of 3 or 6 patients to allow the recommended phase II dose (RP2D) be examined in a total of 9 patients will be used. The dose limiting toxicity (DLT) is defined as Grade 3 or higher (G3+) gastrointestinal (GI) and/or urinary (GU) AEs related to preoperative radiotherapy according to the Clavien-Dindo Classification at 30 days. Three radiation dose levels, 5 Gy, 6 Gy and 6.5Gy are considered. A 3+3 dose escalation plan will be used. At the start of each dose level k ($k=1, 2$, or 3), 3 patients will be enrolled and treated for five days. If none of the 3 patients develop the DLT, the testing dose will escalate to the next level, $k+1$. If 1 of the 3 patients develops the DLT, the current dose will be tested in an additional 3 patients. If no additional patients develop the DLT, the dose will escalate. If 1 of the additional 3 patients develops DLT, i.e. a total of 2 of 6 patients with DLT, the previous dose will be deemed the maximum tolerated dose (MTD) and tested in a total of 9 patients. If ≤ 2 among the 9 patients experience the DLT, this dose will be considered as the RP2D. If ≥ 2 of 3 patients or ≥ 2 of 6 patients develop DLT, the study will stop without MTD if $k=1$ or consider dose level $k-1$ to be the MTD and tested in an additional 3 or 6 patients so that a total of 9 patients are evaluated. If ≥ 3 of 9 patients experience the DLT, the de-escalation will continue. This design ensures that the DLT rate to be $\leq 2/9$ for the RP2D.

In part 2 of the study, additional 21 patients will be enrolled to further examine the safety of the R2PD in a total of 30 patients. The primary safety endpoint will be G2+ GI and/or GU AEs related to preoperative radiotherapy according to the CTCAE v5.0 measured at 1 year. Patients will be continuously monitored to ensure the acute G3+ GU and/or GI AEs based on the Clavien-Dindo Classification at 30 days do not exceed 4 of 18 patients, and 6 of 27 patients.

8.2 Sample Size/Accrual Rate

The sample size for part 1 portion of the study will vary depending on the number of patients that develop the DLT. If no DLTs are seen, we will recruit $3+3+3+6=15$ patients at 5, 6, and 6.5 Gy, respectively. Following the schema above, the maximum number recruited would be 27, which would only occur if 0 of 3 or 1 of 6 patients develop the DLT in dose escalation phase but >2 of 6 or >1 of 3 patients in the expansion cohort develop the DLT, triggering an expanded cohort at a lower dose.

Sample size for part 2 portion of the study will be 30 including the 9 patients from part 1. Having a total of 30 patients in the expansion cohort will allow us to estimate the 1-year G2+ toxicity rate based on CTCAE v5.0 within a 95% CI width of 0.37 and help with the decision making at the end of the trial. For example, an observation of ≥ 8 of the 30 patients having G2+ toxicity at 1-year based on CTCAE v5.0 would suggest that the probability of the toxicity rate being > 0.20 is greater than 80%, which will allow us to make an informative decision on whether the R2PD is worth to be examined at a larger trial.

8.3 *Stratification Factors*

No stratification factors are planned for the primary endpoint.

8.4 *Analysis of Endpoints*

8.5 *Analysis of Primary Endpoints*

Primary endpoints for this study are G3+ GU and/or GI toxicities at 30 days based on Clavien-Dindo Classification (Part 1) and G2+ GU and GI toxicities at 1 year based on CTCAE v5.0 (Part 2). Adverse events based on the two classification systems will be recorded. Descriptive statistics including the number, proportion of patients experience AEs, and 95% confidence interval of the proportion estimate calculated using the Clopper-Pearson method will be summarized. The analysis set will include patients who receive any dose of the preoperative radiation therapy.

8.6 *Analysis of Secondary Endpoints*

Assessment and analysis of secondary endpoints including toxicity and quality of life scores will be descriptive.

8.7 *Interim Analysis*

This study will have interim analyses after every dose in the sense that if any unacceptable dose limiting toxicities are seen, future patients will be recruited at a lower dose.

9 *Adverse Event Reporting Requirements*

Adverse events (AEs) will be recorded REDCAP for the duration of the trial, regardless of whether or not the event(s) are considered related to the trial. All AEs considered related to trial medication will be followed until resolution even if this occurs post-trial.

Adverse events will be recorded for the duration of a patient's participation in the trial. All adverse events (except grade 1 and 2 laboratory abnormalities unless a dose treatment

modification, delay or therapeutic intervention is required), regardless of causal relationship, are to be recorded in the case report form and source documentation. Pre-existing conditions at baseline will be recorded. If a pre-existing condition does not change, it does not have to be reported on subsequent cycles.

The investigator must determine the toxicity of adverse events according to the CTCAE version 5.0 and their causal relationship.

9.1 *Assessing and Recording Adverse events*

An adverse event is defined as any untoward medical occurrence in a patient or clinical investigation participant administered a pharmaceutical product and which does not necessarily have to have a causal relationship with this treatment. An adverse event can therefore be any unfavorable and unintended sign (including an abnormal laboratory finding, for example), symptom, or disease temporally associated with the use of a medicinal product or protocol-specified procedure, whether or not considered related to the medicinal product or protocol-specified procedure.

CTCAE term (AE description) and grade: The descriptions and grading scales found in the revised NCI Common Terminology Criteria for Adverse Events (CTCAE) version 5.0 will be utilized for AE reporting. A copy of the CTCAE version 5.0 can be downloaded from the CTEP web site (<http://ctep.cancer.gov>).

Attribution of the AE:

- Definite – The AE *is clearly related* to the study treatment.
- Probable – The AE *is likely related* to the study treatment.
- Possible – The AE *may be related* to the study treatment.
- Unlikely – The AE *is doubtfully related* to the study treatment.
- Unrelated – The AE *is clearly NOT related* to the study treatment.

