1.1 Primary Objectives

Assess the feasibility of stereotactic body radiotherapy (SBRT) before radical prostatectomy (RP) in patients with high risk prostate cancer. The primary outcome is that a patient can undergo a radical prostatectomy after SBRT without a post-operative dose limiting toxicity (DLT). DLT will be defined as Grade 3 or higher adverse events within 30 days after prostatectomy according to the Clavien-Dindo Classification.

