5.4 Radiation Treatment Planning

Three (3) patients will initially receive 5 Gy for 5 fractions. If patients tolerate the dose and undergo surgery without a post-operative Grade 3 or higher DLT 30 days, another set of 3 patients are selected for the next dose level. If the patients are to develop a post-operative Grade 3 or higher DLT, the trial will accrue additional 6 patients to the previous dose level.

The treatment planning CT will be fused to the T2 sequence of the MRI. The prostate + seminal vesicles (SV) will be contoured as the clinical target volume (CTV). The PTV expansion for the CTV will be 3-5 mm depending on physician discretion.

The bladder, femoral heads, penile bulb will also be contoured as normal structures.

The CTV (prostate + SV) will be treated to the prescribed dose (5, 6, or 6.5) Gy in 5 fractions.

VPrescription Dose (5, 6, or 6.5) Gy (volume of the PTV receiving Prescription (5, 6, or 6.5) Gy should be $\geq 95\%$)

18

- Gy,
1. Rectum: Maximum dose to 1 cc 38.5 Gy, Max dose to 3 cc 34.4 Gy, D53% 24
Max point dose 40 Gy
 2. Bladder: Maximum dose to 1 cc 38.5 Gy, Max point dose 40 Gy
 3. Penile Bulb: No more than 105% of prescription dose; D3cc 25 Gy. This is a
soft constraint.
 4. Femoral heads: Maximum point dose 30 Gy
 5. Small bowel: Maximum point dose 25 Gy
 6. Urethra: Max dose 38.78 Gy

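### The any-dose analysis set does not fit a DLT that can occur only after surgery, and the plan does not say how treated but unoperated patients are counted

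*Combined protocol and SAP*

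**What the plan says.** The combined protocol and SAP gives these elements.

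- **Analysis set (8.5).** "The analysis set will include patients who receive any dose of the preoperative radiation therapy". Reaching surgery is not required.
- **DLT in the objectives (1.1).** "DLT will be defined as Grade 3 or higher adverse events within 30 days after prostatectomy according to the Clavien-Dindo Classification". The clock starts at prostatectomy.
- **Stopping rules (10.2).** The counted event is a post-operative GI or urinary toxicity of grade 3 or higher at 30 days, related to the radiotherapy.
- **DLT in the design section (8.1).** Grade 3 or higher GI or GU "AEs related to preoperative radiotherapy according to the Clavien-Dindo Classification at 30 days". The start of the 30 days is not named. The Part 1 endpoint in 8.5 has the same gap.
- **Primary endpoint (opening of Section 8).** "The primary endpoint for this trial will be successful completion of radical prostatectomy after SBRT without a post-operative DLT of grade 3 or higher". The window here is 30 days from the operation. A patient who is not operated on is not a success.
- **Escalation, two versions.** Section 5.4 opens the next level "If patients tolerate the dose and undergo surgery without a post-operative Grade 3 or higher DLT 30 days". Section 8.1 says only: "If none of the 3 patients develop the DLT, the testing dose will escalate to the next level".
- **Ways to miss surgery (5.7).** Radiotherapy may end early for several reasons, the first being "Patients unable to tolerate radiation therapy"; adverse events, intercurrent illness and withdrawal are also listed.

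No section defines a DLT-evaluable patient, gives a replacement rule, or says how a treated but unoperated patient is counted.

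**The concern.** The trial asks whether prostatectomy is feasible after SBRT. If the 8.5 set is combined with the post-operative DLT of 1.1 and 10.2, a patient who starts radiotherapy and is never operated on adds one to the denominator and nothing to the numerator. The reported 30-day DLT proportion then falls as more patients miss surgery, whatever the reason. The endpoint at the opening of Section 8 would record the same patient as a non-success.

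The cohorts have 3, 6 and 9 patients, so the treatment of one such patient can decide whether a level escalates or is named the RP2D. If the same set governs the Part 2 monitoring, the limits at 18 and 27 patients loosen in the same way.

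**Working it through.** **The plan's own figures.** The limits share one proportion: 2/9 = 4/18 = 6/27 = 22.2%. The Clopper-Pearson method of 8.5 with n = 30 has its greatest width at 15 events, 0.313 to 0.687, which is 0.374 and matches the 0.37 in 8.2. That figure belongs to the one-year endpoint and is not in dispute. The documents give neither a DLT rate nor a non-surgery rate, so both are assumptions below.

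**Set-up.** Let p be the DLT probability among operated patients and q the probability that a treated patient is not operated on, taken as independent.

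- Any-dose set with a post-operative DLT: rate r = p(1 − q)
- Operated patients only: r = p
- Section 8 composite failure: r = 1 − (1 − p)(1 − q)

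The first understates the second by the fraction q. All three agree at q = 0.

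**Chance of meeting the RP2D limit.** P(at most 2 of 9) = (1 − r)^9 + 9r(1 − r)^8 + 36r²(1 − r)^7. With p = 1/3:

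- q = 0, r = 0.333: 0.026 + 0.117 + 0.234 = 0.377
- q = 0.10, r = 0.300: 0.040 + 0.156 + 0.267 = 0.463
- q = 0.20, r = 0.267: 0.061 + 0.201 + 0.292 = 0.554

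**Other decisions, with p = 0.30.** P(escalate) = (1 − r)^3 + 3r(1 − r)^2 × (1 − r)^3. The last column is a single look at 18 patients against the 10.2 limit.

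| q | r on any-dose set | P(escalate) | P(at most 2 of 9) | P(5 or more of 18) |
|---|---|---|---|---|
| 0 | 0.30 | 0.494 | 0.463 | 0.667 |
| 0.10 | 0.27 | 0.557 | 0.545 | 0.559 |
| 0.20 | 0.24 | 0.622 | 0.629 | 0.441 |

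The q = 0 row is also what the same numbers of operated patients would give at any q.

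**One patient at the boundary.** Take 9 treated, 1 unoperated and 2 DLTs.

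- Any-dose set: 2/9 = 22.2% (95% CI 2.8% to 60.0%)
- Operated only: 2/8 = 25.0% (3.2% to 65.1%)
- Section 8 composite failures: 3/9 = 33.3% (7.5% to 70.1%)

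The first meets the limit of at most 2 in 9. The third, if it were the count used, would reach 3 of 9. At an assumed q of 0.10, the chance that at least one of 9 treated patients is unoperated is 1 − 0.9^9 = 0.61.

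**The case against.** A reader might infer that the plan counts every failure to reach surgery as DLT-free, so that the DLT rate is biased downward throughout. The documents do not support that much.

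- No section states such a rule. It follows only from combining 8.5 with 1.1 and 10.2, while Section 5.4 and the opening of Section 8 point the other way.
- Sections 8.1 and 8.5 do not anchor the 30 days to surgery. On that wording a severe pre-operative GI or GU event related to radiotherapy might count as a DLT.
- The any-dose sentence sits with the descriptive analysis. Nothing expressly ties it to the 3/6/9 or 18/27 counts, and 8.1 refers to 9 patients being evaluated.
- DLTs among all treated patients is a legitimate quantity if it is the declared target.
- A starker contrast is available but mixes two endpoints. If 10% are kept from surgery by toxicity and 10% of operated patients have a DLT, the post-operative DLT rate per treated patient is 0.9 × 0.1 = 9% and composite failure is 0.1 + 0.9 × 0.1 = 19%. Much of that gap is the change of endpoint, not bias.
- Non-surgery may be rare. Eligibility requires fitness for prostatectomy and excludes unwilling patients, and surgery is scheduled less than 4 weeks after radiotherapy. Adverse events are recorded whatever their cause and reviewed at every dose level, and the DSMB can recommend modification or termination.

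These points limit the size and certainty of the effect. They do not remove the mismatch. The safeguards make toxicity visible but do not say how the patient is counted. The unanchored wording adds a second possible numerator and still leaves a patient who misses surgery without a grade 3 GI or GU event in the denominator only. Section 8 declares a target other than DLTs per treated patient.

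**Conclusion.** The point holds as a conflict between sections. Applied as written, the 8.5 set with the 1.1 and 10.2 DLT gives a result for unoperated patients that contradicts the plan's own primary endpoint and its 5.4 escalation condition.

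The exposure covers the Part 1 30-day DLT estimate and, only if the same set is used there, the 3/6/9 and 18/27 counts. The Part 2 endpoint, grade 2 or higher CTCAE toxicity at one year, does not need surgery to occur and is unaffected.

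The relative understatement against operated patients equals the non-surgery rate, so it is zero if all are operated on. The rise in P(at most 2 of 9) from 0.38 to 0.46 or 0.55 rests on an assumed DLT rate of 1/3, assumed non-surgery of 10% or 20%, and independence of the two. It illustrates sensitivity and does not predict what this trial will see.

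**What to change.** 1. Analyse the composite from the opening of Section 8 on everyone who starts SBRT, with patients who do not complete prostatectomy as non-successes, as that text already defines.
2. In 8.5, define a DLT-evaluable set for the 30-day DLT rate and state when the 30 days begin. Keep the any-dose set for the adverse event tables.
3. Reconcile Sections 1.1, 5.4, 8 (opening), 8.1, 8.5 and 10.2 on how treated but unoperated patients enter the escalation, RP2D and stopping counts, and on whether they are replaced. The choice of clinical rule is the sponsor's.

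The cost is protocol and SAP wording and possibly a less favourable reported success rate. If the sponsor chooses replacement, a few extra patients may be needed, to be checked against the accrual ceiling of 45.

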9.1.1 Evaluating Adverse Events

An investigator who is a qualified physician will evaluate all adverse events according to the NCI Common Terminology for Adverse Events (CTCAE), version 5.0. Any adverse event which changes CTCAE grade over the course of a given episode will have each change of grade recorded on the adverse event case report forms/worksheets. All adverse events regardless of CTCAE grade must also be evaluated for seriousness.

9.1.2 Recording of Adverse Events

All adverse events will be recorded on a patient specific AE log. The AE log will be maintained by the research staff and kept in the patient's research chart. The AEs are documented in REDCAP database.

9.1.3 Reporting of AE to WCM IRB

All AEs occurring on this study will be reported to the IRB according to the IRB policy, which can be accessed via the following link:

http://researchintegrity.weill.cornell.edu/forms_and_policies/forms/Immediate_Reporting_Policy.pdf.

9.2 Definition of SAE

SAE's include death, life threatening adverse experiences, prolonged hospitalization, disability or incapacitation, overdose, congenital anomalies and any other serious events that may jeopardize the subject or require medical or surgical intervention to prevent one of the outcomes listed in this definition.

9.2.1 Reporting of SAE to IRB

All SAEs occurring on this study will be reported to the IRB according to the IRB policy, which can be accessed via the following link:

http://researchintegrity.weill.cornell.edu/forms_and_policies/forms/Immediate_Reporting_Policy.pdf.

10 Data and Safety Monitoring Plan (DSMP)

The study will be monitored internally by the study teams in Radiation Oncology and Urology. Adverse events will be reviewed at every dose level.

The WCMC Data and Safety Monitoring Board (DSMB) is the central monitoring board for this study. The WCMC Cancer Institute DSMB is the local monitoring board for WCMC patients. This study will be conducted in accordance with the guidelines in the 2001 NCI approved data Safety and Monitoring plan for the WCMC Cancer Institute and with the WCMC approved data Safety and Monitoring plan for the WCMC Cancer Institute. Reports to the DSMB will include the following information: accruals, targets, responses, adverse events and evidence of reporting to appropriate review committees. The WCMC Data and Safety Monitoring Board (DSMB) will review the IRB approved protocol, the data and safety monitoring plan and any stopping guidelines during protocol initiation. During the course of the study, the DSMB will

review cumulative study data twice a year to evaluate safety, efficacy, study conduct, and scientific validity and integrity of the trial. The WCMC DSMB may also convene as needed if stopping criteria are met or other safety issues arise that the Principal Investigator and/or IRB would like the WCMC DSMB to address.

